**Profiling the determinants of recovery to establish novel rehabilitation guidelines to improve clinically relevant and patient-reported outcomes in the post-COVID-19 period across 3 individual countries.**

Background	
The value of clinical cardiopulmonary exercise testing (CPET) within healthcare settings has been established in the last decade. CPET methods remain highly relevant in the COVID-19 endemic phase and should be used to assess those recovering from COVID-19 infection. This diagnostic tool could play an integral role in disease prognostication and evaluate the integrative response to incremental exercise. Data from such assessments can enable practitioners to characterise cardio-respiratory fitness and identify reasons for physical impairment or abnormal cardio-respiratory function. More than 50% of patients admitted to hospital will experience cardiorespiratory issues and significant morbidity during their recovery and will require significant rehabilitative support. In this context, measurements obtained from an assessment of cardio-respiratory responses to physiological stress could provide insight regarding the integrity of the pulmonary-vascular interface and characterisation of any impairment or abnormal cardio-respiratory function. Current approaches to rehabilitation are being developed on existing knowledge from Severe Acute Respiratory Syndrome (SARS) and Acute Respiratory Distress Syndrome (ARDS) related illness. These provide important insight but do not provide insight into the novel challenges provided by COVID-19.
 
We bring together three clinical and academic research centres from around the world that collaborate as part of the Healthy Living for Pandemic Event Protection international network to conduct a minimum of 150 2-day CPET tests in patients that hospitalised with COVID-19. Patients will be engaged in testing in the UK (led by [name] from the Human Science Research Centre, Derby and [name] from the Research and Innovation for post-COVID-19 Rehabilitation centre, Sheffield), USA (led by [name] and [name] at the University of Illinois at Chicago) and India (led by [name] and [name] at the Ramaiah Medical College, Bangalore). All tests will be conducted following standardised procedures documented by the American College of Sports Medicine.

Acronym	HL-PIVOT-LCR
Short title	HL-PIVOT: Long COVID Rehabilitation

Description of interventions	Consecutive day 2 day CPET and follow up for 7 days for subjective feelings/fatigue.
Duration of study	
Study Duration:
 
 
- Total trial duration 12 months 
 
○ Recruitment 6 months (November 2022 to April 2023)
 
○ Data Collection (November 2022-April 2023)
 
○ Analysis and reporting: 4 months (April 2023-July 2023)
 
 
 
- Participant Duration: 3 sessions (1 Familiarisation, 2 CPET on consecutive days) and 1 week follow up
 

Randomisation and blinding	None

Study Investigators	
Chief Investigator: [name] Senior Lecturer in Exercise Physiology School of Human Sciences University of Derby, UK	Principle Investigator (Sheffield, UK) [name] Senior Research Fellow Advanced Wellbeing Research Centre Sheffield Hallam University, UK
Principle Investigator (Chicago, USA) [name] Clinical Associate [name] of Physical Therapy University of Illinois at Chicago Chicago, USA	Principle Investigator (Bengaluru, India) [name] [name] Assistant Professor, Department of Physiotherapy Ramaiah Medical College, Bengaluru, India
Co-Investigator: [name] [name] of Physical Therapy University of Illinois at Chicago Chicago, USA	Co-Investigator: [name] Lecturer in Exercise Physiology School of Human Sciences University of Derby, UK
Co-Investigator: [name] Director, Advanced Wellbeing Research Centre Sheffield Hallam University	Co-Investigator: [name] Consultant Respiratory Physician University Hospitals of Derby and Burton Derby, UK
Co-Investigator: [name] Assistant [name] of Physical Therapy University of Illinois at Chicago Chicago, USA	Co-Investigator: [name] School of Human Sciences University of Derby
Co-Investigator: [name] Researcher, Advanced Wellbeing Research Centre, Sheffield Hallam University.	Co-Investigator: [name], Principal Research Fellow, Advanced Wellbeing Research Centre, Sheffield Hallam University.
Co-Investigator: [name], Associate Professor, Advanced Wellbeing Research Centre, Sheffield Hallam University.	Co-Investigator:

## 1.0 Background

The value of clinical cardiopulmonary exercise testing (CPET) within healthcare settings has been established in the last decade [5]. CPET methods remain highly relevant in the COVID-19 endemic phase and should be used to assess those recovering from COVID-19 infection. This diagnostic tool could play an integral role in disease prognostication and evaluate the integrative response to incremental exercise. Data from such assessments can enable practitioners to characterise cardio-respiratory fitness and identify reasons for physical impairment or abnormal cardio-respiratory function. More than 50% of patients admitted to hospital will experience cardiorespiratory issues and significant morbidity during their recovery and will require significant rehabilitative support. In this context, measurements obtained from an assessment of cardio-respiratory responses to physiological stress could provide insight regarding the integrity of the pulmonary-vascular interface and characterisation of any impairment or abnormal cardio-respiratory function. Current approaches to rehabilitation are being developed on existing knowledge from Severe Acute Respiratory Syndrome (SARS) and Acute Respiratory Distress Syndrome (ARDS) related illness. These provide important insight but do not provide insight into the novel challenges provided by COVID-19.

We bring together three clinical and academic research centres from around the world that collaborate as part of the Healthy Living for Pandemic Event Protection international network to conduct a minimum of 150 2-day CPET tests in patients that hospitalised with COVID-19. Patients will be engaged in testing in the UK (led by [name] from the Human Science Research Centre, Derby and [name] from the Research and Innovation for post-COVID-19 Rehabilitation centre, Sheffield), USA (led by [name] and [name] at the University of Illinois at Chicago) and India (led by [name] and [name] at the Ramaiah Medical College, Bangalore). All tests will be conducted following standardised procedures documented by the American College of Sports Medicine.

## 2.0 Aims and Objectives

- Evaluate the integrative response to incremental exercise and increase diagnostic information relating to post-COVID-19 morbidity.
- Assess cardio-respiratory responses to physiological stress and provide insight regarding the integrity of the pulmonary-vascular interface and characterization of any impairment or abnormal cardio-respiratory function.

### 2.1 Primary Aim

- Evaluate the integrative response to incremental exercise and increase diagnostic information relating to post-COVID-19 morbidity.

### 2.2 Secondary Aims

- Examine the relationship between COVID-19 symptom prevalence and exercise tolerance
- Examine the prevalence of post-exertional malaise in people with long covid.
- Examine the role of vaccination history (COVID-19) on exercise tolerance.

- Assess cardio-respiratory responses to physiological stress and provide insight regarding the integrity of the pulmonary-vascular interface and characterization of any impairment or abnormal cardio-respiratory function.

## 3.0 Study Design

A multicentre, cross-sectional, observational study.

#### International Sites:

##### **Ramaiah Medical College, Bengaluru, India**

In India, the study will be conducted at the Centre for Rehabilitation, and the Department of Physiotherapy at the Ramaiah Medical College Hospitals. Patients will be recruited through telephonic follow-up of patients discharged from the Ramaiah Medical College Hospitals as well as through the Post COVID Clinic of at Ramaiah Memorial Hospital.

##### **University of Illinois, Chicago.**

In the USA, study visits will be conducted at the University of Illinois' Physical Therapy Faculty Practice, Chicago, IL, USA. Patients will be recruited from the University of Illinois Hospital through the pulmonology and cardiology clinics as well as through word of mouth and social media.

### 3.2 Sample Size

A minimum of 150 patients admitted to hospital with a positive COVID-19 infection will be recruited for WP2. Patients for WP2 will be recruited to the study from three international centres (UK; led by [name], Royal Derby and Burton Hospital Trust and the Research and Innovation for post-COVID-19 Rehabilitation Centre; USA led by [name], University of Illinois at Chicago; India led by [name] , Ramaiah Medical College, Bengaluru. In line with the consensus in current literature, patients will not be treated in intensive care units. Those requiring rigorous treatment via intensive care units will experience profound complications in the post-COVID-19 period and trials involving these groups have already been established by clinical centres (Imperial

College London). Currently the Office for National Statistics estimates that 1.2 million people in the UK are suffering with Long COVID.

### 3.3 Eligibility and Exclusion

Eligibility criteria includes:

- Aged 18 to 65 years old
- Diagnosed with COVID-19
- Still suffering from symptoms of COVID-19, 3 months after initial infection
- Sufficient English language comprehension and cognitive ability to understand the study protocol, give informed consent and follow instructions.

Exclusion criteria includes:

- <18 years of age
- Admitted to or received treatment from Intensive Care Units
- Unconfirmed COVID-19 test diagnosis
- Unable to understand verbal or written information in English
- Achieving a grade 0 or 1 on the PCFS.
- Unstable angina
- Uncontrolled hypertension, that is, resting systolic blood pressure (SBP) >180mmHg, or resting diastolic blood pressure (BP) (DBP) >110mmHg
- Orthostatic blood pressure drop of >20 mmHg with symptoms
- Significant aortic stenosis (aortic valve area 120 bpm)
- Acute pericarditis or myocarditis
- Decompensated HF
- Third degree (complete) atrioventricular (AV) block without pacemaker
- Recent embolism
- Acute thrombophlebitis
- Resting ST segment displacement (>2 mm)
- Uncontrolled diabetes mellitus
- Severe orthopaedic conditions that would prohibit exercise
- Other metabolic conditions, such as acute thyroiditis, hypokalaemia, hyperkalaemia or hypovolaemia (until adequately treated)
- Severe grade 3 rejection (cardiac transplantation recipients Appendix N).

### 3.4 Approach/Recruitment

Participants will be recruited from existing patient databases and Long COVID clinics in the UK as well as through social media.

### 3.5 Ethical Considerations

#### 3.5.1 Consent

Eligible patients will be identified at the designated PIC sites (STH, Sheffield; UIC, USA and Ramaiah, India) by individuals knowledgeable about the research. The researcher will introduce themselves to the patient and/or patient representatives and explain the nature of their visit to the patient. The researcher will proceed, if the patient agrees, to discuss the nature, objective, risks, and benefits of the proposed research. This will include the provision of written information regarding the research study, implications, expected outcomes, risks, and benefits. The patient will be allowed to ask questions throughout this process.

Once patients have indicated their willingness to participate in the research, they will be invited to a session at their local site. Consent will be obtained by members of the research team and documented using the study consent form. Informed consent will be obtained before the participant undergoing any activities that are specifically for the study. All study documentation (i.e. participant information sheet, participant consent form) will be kept in the Trial Master File.

The right of the patient to refuse to participate in the study without giving any reason must be respected. Equally, the patient will be free to withdraw their consent to participate in the study without providing any reasons and without prejudicing his or her further treatment.

#### 3.5.2 Deception

No deception will occur within this project. All research aims and procedures will be articulated to the patient and included within the PIS.

#### 3.5.3 Debriefing

All participants will be given the opportunity to hear about the results of the study in the form a short summary upon completion. This will be provided by the chief investigator and all participants will be able to 'opt out' of this opportunity should they wish to.

Regardless all participants will be thanked for their participation at the final visit.

#### 3.5.4 Withdrawal from the investigation

Patients will be free to withdraw their consent to participate in the study at any time without providing any reasons and without prejudicing his or her further treatment.

Withdrawal from the investigation can be done at any time by contacting the chief investigator and/or members of the study team using the contact details provided on the PIS.

### *3.5.5 Anonymity and Confidentiality*

Information related to participating in the study will be kept confidential and managed in accordance with the Data Protection Act, NHS Caldecott Principles, The Research Governance Framework for Health and Social Care and the conditions of Research Ethics Committee approval.

Staff involved in the study will ensure that all participants' confidentiality is maintained at all times.

On all study documentation participants will be identified only by a unique patient study identification number on the CRF and central electronic database (Redcap).

### *3.5.6 Protection of Participants*

All components of the research activity has been approved by local NHS REC and the HRA (via the IRAS system) and all planned activities have also been approved by the clinical research support team. All participants will be informed and aware of the expectations taking part in the research and will be provided with regular opportunity to ask questions relating to their involvement.

### *3.5.7 Observation Research*

This study will comprise of a 2-week cohort observation. Whilst the study design is adopting an observational approach participants will be made aware of all research activities.

### *3.5.8 Giving Advice*

No advice will be provided by the research team. If patients raise questions relating to clinical issues relating to their health, they will be directed to contact their GP.

The PIS also provides links to NHS helpline/advice pages which patients will be directed too.

Research will not be undertaken in public places.

### *3.5.9 GDPR - Collecting Personal Data*

Researchers will be collecting data from participants in this study. This data has been specifically chosen to achieve the aforementioned aims and study outcomes and in the public interest of enhancing clinical understanding academic research. No information that is not directly associated with the research questions will be collected.

This is the legal basis on which we are collecting your data and while this allows us to use your data, it also means we have obligations towards you to:

- Not seek more information from you than what is essential and necessary for the study;
- Make sure that you are not identified by the data by anonymising it using ID codes;
- Use your anonymised data only for the purposes of this study and for any relevant publications that arise from it;

- Store data safely in password-protected databases to which only the named researchers have access;
- Not keep your information for longer than is necessary (usually for seven years);
- Safely destroy your data by shredding or permanently deleting them.
- Researchers on the project with access to the data are supervised by highly qualified and experienced staff and have been very careful to ensure the security of your data.

The study was approved for its ethical standards by Health Research Authority (IRAS 313936) and the University of Derby Human Sciences Research Ethics Committee.

### *3.5.10 Basis for Collecting Data*

Consent

### *3.5.11 Data Retention*

Study records will be stored for 15 years according to the Research & Innovation Office SOP for archiving, in a secure off-site storage. Direct access to source documents and data will be granted to authorised representatives from the sponsor, host institution and the regulatory authorities to permit trial-related monitoring, audits, inspections and reviews.

### *3.5.12 Rights of Data Subject*

All rights have been addressed via the utilisation of the GCP guidelines and via HRA approval.

## **4.0 Study Protocol**

Each test will be interpreted following published guidelines provided by the American College of Sports Medicine. Upon the conclusion of each test, the key descriptive characteristics and findings will be recorded to facilitate the use of cohort analyses. Data will be stratified according to the demographic (age, gender, ethnicity, pre-COVID-19 functional status and important physiological parameters for a given workload (absolute and relative oxygen consumption or  $VO_2$  peak,  $O_2$  pulse, alveolar-arterial  $O_2$  gradient, arterial to end-tidal  $CO_2$  difference and the relationship between carbon dioxide output and ventilation ( $V_E/VCO_2$  slope))). These approaches will be used to identify differences, trends and patterns in key defining variables that might lead to longstanding impairment/morbidity. Study day 1 will be conducted 7-10 days post baseline measures to ensure no symptoms of post exertional malaise and/or excessive fatigue from baseline assessments. Patients will wear accelerometers during this period to compare baseline and follow up.

Baseline	Session 2	Session 3 (+1 day)	7 Day follow up
Anthropometrics Questionnaires Symptom Profile* Lung Function TUG 6MWT	Symptom Profile* ECG Resting HR + BP CPET Lactate and BP Recovery following CPET HRV	Symptom Profile* ECG Resting HR + BP CPET Lactate and BP Recovery following CPET HRV	Accelerometry Patient Log/Diary HRV

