### **4.1.3 Functional Status**

Two different assessments of lower extremity functional capacity will be conducted at each visit these are (A) the 6-minute walk test (6MWT) and (B) the timed up and go test (TUG). The 6MWT is a standardised and widely used measure of functional status in individuals with chronic disease such as chronic obstructive pulmonary disease, cystic fibrosis, congestive cardiac failure, peripheral vascular disease, and elderly. It has been previously used to assess response to interventions and predict morbidity and mortality. Participants will be given a shortened practice attempt (1-2 minutes) at the beginning of each of their assessment visits. This will not be recorded but will be performed to allow familiarisation with the assessment and repeated at each visit for

consistency. Patients suffering from excessive fatigue/Post exertional malaise from the 6MWT will be excluded from the study to prevent further onset of these symptoms.

The TUG is reliable and reproducible and has been validated as a predictor of frailty and risk of falls in elderly adults. The TUG has several advantages over other measures, mainly its reproducibility and shorter assessment time. Its use at predicting functional status following pneumonia has not been assessed previously.

Participants will also be asked to self-report their return to functional activity and employment at each contact with the research team (telephone consultations and follow-up visits.) Each participant will be asked at each contact with the research team if they have returned to perform their activities of daily living to the same level as 6 weeks before admission, and if they have returned to their occupation (if employed.) The patient-reported date of return to these activities will also be recorded.

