## 4.2 Follow-up Assessments

Using a custom developed application alongside commercially available heart rate monitoring devices, participants will be asked to provide accelerometry (asked through the participants phone), heart rate variability (iHeart) and a subjective wellness score for each day following baseline and CPET investigations each for a period of 3 days. This custom developed software has been developed at the Advanced Wellbeing Research Centre to provide objective and subjective assessment of fatigue in people suffering with long covid and has successfully been piloted with over 200 individuals. Where smartphone data is not possible, individuals will be asked to wear an accelerometer and subjectively report their wellness through patient diary.

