### 4.4.3 Post-Exertional Malaise

Post exertional malaise has been identified in patients with long covid especially with incremental exercise and exertion. We will screen for individuals' experiences PEM

prior to the study and follow up with individual participants following baseline measurement sessions before proceeding with repeated day CPET. Those individuals who show symptoms of PEM will be provided with guidance of pacing and provided with access to published materials around managing fatigue as per UK NHS long covid clinic guidance (World Physiotherapy, 2021).

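### All daily activity, HRV and wellness recording before CPET starts after the 6MWT, so the pre-CPET reference may carry post-exertional effects: wholly under Section 4.2, partly under Section 4.0

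*Protocol*

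**What the plan says.** The schedule in Section 4.0 lists the content of the baseline session as "Anthropometrics Questionnaires Symptom Profile* Lung Function TUG 6MWT". Accelerometry and the diary appear only in the follow-up column. HRV appears there and at sessions 2 and 3.

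The text of Section 4.0 places the first CPET "7-10 days post baseline measures to ensure no symptoms of post exertional malaise and/or excessive fatigue from baseline assessments". The next sentence reads: "Patients will wear accelerometers during this period to compare baseline and follow up".

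Section 4.2 describes the app-based recording differently. Accelerometry is to be supplied together with "heart rate variability (iHeart) and a subjective wellness score for each day following baseline and CPET investigations each for a period of 3 days".

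Two other passages treat the baseline session as a possible trigger of symptoms. Section 4.1.3 states: "Patients suffering from excessive fatigue/Post exertional malaise from the 6MWT will be excluded from the study to prevent further onset of these symptoms". Section 4.4.3 has staff "follow up with individual participants following baseline measurement sessions before proceeding with repeated day CPET".

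The synopsis (description of interventions) and the schedule table give the follow-up as 7 days, against 3 days in Section 4.2.

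**The concern.** A reference for a response to exercise should describe the patient in a recovered state. Here all daily recording before CPET begins after a session with a walk test, inside the interval the protocol sets aside for the effects of that session to wear off. If activity, HRV or wellness is lowered on those days, the contrast between post-CPET and reference days comes out too small.

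How common post-exertional malaise is in this population is a secondary aim (Section 2.2), and Section 4.2 presents the app as the tool for assessing fatigue. The daily recordings are therefore natural evidence for that aim. The understatement would fall on patients with a mild reaction to the walk test, who stay in the study because their reaction is not severe enough for exclusion under Section 4.1.3.

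Part of this cannot be repaired at the analysis stage. A SAP can choose which recorded days to use, but it cannot supply HRV or wellness values that were never requested.

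**Working it through.** The protocol gives no figure for this comparison, so there is none to reproduce. The check sets the recording windows against the timeline and then illustrates the possible attenuation.

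**Timeline (day 0 = baseline session with 6MWT and TUG)**
- Before day 0: no daily recording (schedule table, Section 4.0).
- Session 2: day 7 to day 10 (Section 4.0).
- Window under Section 4.2: days 1 to 3. All 3 of 3 days lie inside the gap. Recording stops 7 − 3 = 4 to 10 − 3 = 7 days before session 2.
- Window under Section 4.0, accelerometers only: the whole 7 to 10 days, starting straight after the 6MWT but including later days on which recovery is presumed.

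**Formula**

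Let D be the true fall after CPET from the recovered level. Let f be the carry-over from the baseline session as a fraction of D, in the same direction, on c affected days out of w reference days. The reference mean then lies f × D × c/w below the recovered level, so

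observed contrast = D × (1 − f × c/w),

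and the attenuation is f × c/w.

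**Inputs**
- w = 3 (Section 4.2), or w = 7 to 10 (Section 4.0).
- c = 3. Under Section 4.2 this means all reference days are affected. Under Section 4.0 it means carry-over lasts 3 days. Assumption.
- f = 0.25 to 0.50. Assumption; the documents give no value.

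**Results**

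| f | 3-day window (c/w = 3/3) | 10-day average (3/10 = 30%) | 7-day average (3/7 = 43%) |
|---|---|---|---|
| 0.25 | 25% | 7.5% | 10.7% |
| 0.50 | 50% | 15% | 21% |

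The direction is the same under both readings; the size differs by a factor of 7/3 = 2.3 to 10/3 = 3.3.

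**Is a cleaner window available?** The last 3 days before session 2 are days 4 to 6 if session 2 falls on day 7, and days 7 to 9 if it falls on day 10. Even at the shortest gap they do not overlap days 1 to 3. Accelerometers cover them under Section 4.0. HRV and wellness prompts under Section 4.2 do not.

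**The case against.** Much of the case on the other side stands.

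- **The accelerometer window is wider than 3 days.** Read in context, Section 4.0 has accelerometers worn through the whole gap, including its later days. If that passage governs, recovered-state activity data are collected, and choosing the reference days could be left to a SAP. This limits the point for activity. It does not help HRV or wellness, which only Section 4.2 schedules as daily measures before CPET.
- **The baseline comparison is stated for accelerometry only.** A reader might infer that the protocol measures the CPET effect on HRV and wellness against the post-6MWT days. No passage says so. Section 4.2 only says when these are recorded, and the days after baseline may also serve the check before CPET described in Section 4.4.3. What stands is conditional: if such a contrast is made, no better daily reference exists.
- **There are safeguards.** Patients with clear reactions to the 6MWT are excluded, so the bias cannot be largest in them. The symptom profile is repeated at session 2, after the gap. HRV is also listed there, though its timing relative to the CPET is unclear. Neither supplies free-living activity or daily wellness.
- **The gap is a precaution.** A reader might take it as a forecast that symptoms will follow the 6MWT. The text only guards against that possibility.
- **No sample-size consequence follows.** One might turn the attenuation into extra patients needed. Section 3.2 has no power calculation and Section 4.5 specifies no activity or HRV contrast, so there is nothing to inflate. A larger sample would not remove a bias in any case.

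**Conclusion.** The point holds as a weakness in data collection that is cheap to avoid. Followed as written, Section 4.2 yields no daily HRV or wellness data from a recovered state before CPET, and its 3-day activity window lies wholly in the possibly affected period. Under Section 4.0 only part of the activity reference is affected. The two sections disagree, and the protocol does not say which governs.

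Any comparison of post-CPET days with these days would tend to understate the CPET response in milder responders. The size is unknown: the ranges in the working rest on an assumed f, on carry-over having the same direction as the CPET response, and, for the longer window, on a carry-over of 3 days. If there is no carry-over, there is no bias.

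The documents do not support the stronger statement that the CPET effect is measured throughout against an already exerted reference. They support a conditional bias on evidence relevant to a secondary aim, which justifies changing the recording plan without questioning the rest of the design.

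**What to change.** 1. Reconcile the recording windows: the 7-day follow-up in the synopsis and schedule table, wear through the 7 to 10 day gap in Section 4.0, and 3 days after each investigation in Section 4.2.
2. Define the pre-CPET reference as the last 3 days before session 2, for activity, HRV and wellness alike.
3. Prompt the app (or the diary, where no smartphone is used) for HRV and wellness on those 3 days, and confirm that activity recording covers them.
4. Keep days 1 to 3 after the baseline session as a separate window describing the response to the 6MWT.

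The cost is three more days of prompts per participant, a slight added burden, and a revised analysis window. No extra visit or device is needed. The remedy relies on the protocol's own premise that the gap is long enough for recovery; the separate days 1 to 3 window lets the investigators look at that.
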